Methodology	Monitoring of occurrence of pregnancies and evaluating the menstrual blood loss in the HMB subgroup

Type of control	Uncontrolled study
Number of subjects	Approximately 360 subject to enter the treatment period
Primary variable	Occurrence of pregnancies
Time point/frame of measurement for primary variable(s)	Treatment period of up to 3 years (total time of Mirena use up to 8 years).
Plan for statistical analysis	
Analysis of primary variable:
 
Primary Analysis: The Pearl index (PI) will be calculated as the number of pregnancies within years 6-8 of Mirena use per 100 women years, and the corresponding 2-sided 95% confidence interval will be provided.
 
Secondary Analysis: The cumulative failure rate, i.e., the probability of getting pregnant will be calculated using the Kaplan Meier method in addition to the calculation of PIs.

Table of contents

Cover page of the integrated protocol.....	1
1. Title page	2
Signature of the sponsor’s medically responsible person.....	3
Signature of principal investigator	4
2. Synopsis.....	5
Table of Tables	11
Table of Figures.....	12
List of abbreviations	13
3. Introduction.....	15
4. Study objectives.....	19
5. Study design.....	19
6. Study population	21
6.1 Inclusion criteria	22
6.2 Exclusion criteria	22
6.3 Justification of selection criteria.....	23
6.4 Withdrawal of subjects from study.....	24
6.4.1 Withdrawal	24
6.4.2 Replacement	26
6.5 Subject identification.....	26
7. Treatments.....	26
7.1 Treatments to be administered.....	26
7.2 Identity of study treatment.....	26
7.3 Treatment assignment.....	26
7.4 Dosage and administration	27
7.4.1 Removal of Mirena	27
7.5 Blinding.....	27
7.6 Drug logistics and accountability	27
7.7 Treatment compliance	27
8. Non-study therapy	28
8.1 Concomitant therapy	28
8.2 Post-study therapy	28
9. Procedures and variables	28
9.1 Tabular schedule of evaluations	28
9.2 Visit description.....	34
9.2.1 Optional pre-screening contact	35
9.2.2 Screening – Visit 1	35

9.2.3	Baseline – Visit 2	36
9.2.4	6-month visit – Visit 3.....	36
9.2.5	12-month visit – Visit 4 (End of Year 6 of Mirena use)	37
9.2.6	18-month visit – Visit 5.....	37
9.2.7	24 –month visit – Visit 6 (End of Year 7 of Mirena use)	38
9.2.8	30-month visit – Visit 7.....	38
9.2.9	36-month visit, EOT – Visit 8 (End of Year 8 of Mirena use)	39
9.2.10	3-week follow-up call (EOS)	39
9.2.11	3-month follow-up contact for post-study pregnancies	39
9.2.12	12-month follow-up contact for return-to-fertility	40

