10.3.1 Variables

10.3.1.1 Efficacy variables

10.3.1.1.1 Primary efficacy variable

This section was changed in Amendment 1, see Section [15.1.1.1](#) and [15.1.1.26](#).

The primary efficacy variable is the occurrence of pregnancy within years 6 thru 8 of Mirena use. However, for the analysis after 6 years of Mirena use, the primary efficacy variable is the occurrence of pregnancy within year 6 of Mirena use, and for the analysis after 7 years, the primary efficacy variable is the occurrence of pregnancy within years 6 thru 7 of Mirena use.

The Pearl Index (PI) is defined as the number of pregnancies per 100 woman years. The Pearl Index will be analyzed for the 'extension treatment period' starting at Day 1 of Year 6 of Mirena use, i.e., exposure and pregnancies between the baseline visit and Day 1 of Year 6 of Mirena use will be excluded. The following PIs will be calculated:

- '1-year PI' (sixth year)', PI obtained in the sixth year of treatment, i.e., number of pregnancies that occurred during the sixth year of treatment divided by time the women were under risk of getting pregnant in the sixth year of treatment.
- '2-year PI' (sixth and seventh year)', PI obtained in the sixth and seventh year of treatment, i.e., number of pregnancies that occurred during the sixth and seventh year of treatment divided by time the women were under risk of getting pregnant in the sixth and seventh year of treatment.
- '3-year PI' (sixth, seventh and eighth year)', PI obtained in the sixth, seventh and eighth year of treatment, i.e., number of pregnancies that occurred during the sixth, seventh and eighth year of treatment divided by time the women were under a risk of getting pregnant in the sixth, seventh and eighth year of treatment.

Furthermore, the following PI will be analyzed for the entire study period starting at baseline visit, i.e., exposure and pregnancies between the baseline visit and Day 1 of Year 6 of Mirena use will be included:

- 'Overall PI', PI obtained during the whole study, i.e., number of pregnancies that occurred during the entire study period starting at baseline visit divided by the time the women were under a risk of getting pregnant.

The exact rules regarding how the exposure time will be calculated are given in Section [10.3.2.1](#).

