A pregnancy will be allocated to the time period(s) that are relevant for the calculation of the PIs described above, e.g., a pregnancy that occurs on day 400 will be relevant for the 7th year PI, the two years PI (6th and 7th year), the three years PI (6th, 7th and 8th year), and the overall PI. Pregnancies that occur before Day 1 Year 6 of Mirena use will not count for the 1-year PI, 2-year PI and 3-year PI. Pregnancies that occur after the Mirena was removed or an expulsion was realized will not count for any PI.

It should be noted that e.g., pregnancies that occur after partial expulsion, but before Mirena removal will count for the PIs.

Furthermore, it should be noted that pregnancies that occur within 7 days after the end of exposure will count for the PIs.

Exposure times to be subtracted:

Subjects who apply additional concomitant contraception are not in risk or are under a lower risk of getting pregnant than subjects who do not apply additional contraception. In case a subject uses concomitant contraceptive methods (e.g., condoms to prevent STD); the respective 28-day reference period(s) of additional contraceptive method use will be excluded from the exposure time, unless a pregnancy occurred in that 28-day reference period.

Primary analysis

The primary method for the evaluation of the occurrence of pregnancy is the Pearl index defined as the number of pregnancies per 100 women years.

The PIs and the corresponding 2-sided 95 % confidence interval (CI) will be calculated using the model specified below.

Mathematical model for the calculation of the PI:

By assuming that the number of pregnancies follows a Poisson-distribution, the point estimate and the 95 % CI for the PI can be calculated as follows:

$$PI = x/E,$$

lower 95 % confidence limit of PI = $0.5 \times \chi^2_{(0.025, 2x)} / E$

upper 95 % confidence limit of PI = $0.5 \times \chi^2_{(0.975, 2(x+1))} / E$

where x = number of pregnancies,

E = exposure in 100 woman years (one woman year is 365 days of treatment exposure),

$\chi^2_{(\alpha, df)}$ is the alpha quantile from χ^2 -distribution with df degrees of freedom.

The primary analysis set will be the PAS Year 6 (for the analysis after 6 years), the PAS Year 7 (for the analysis after 7 years) and the PAS Year 8 (for the final analysis after 8 years), respectively. Furthermore, analyses will be repeated for the FAS.

Secondary analysis

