10.4 Determination of sample size

The sample size calculation is not based on statistical considerations. It is targeted to have 200 women completing the 8th year of treatment with Mirena. With an estimated dropout rate of 15%, the total number of women to be enrolled into the study treatment phase would be 350.

In order to account for women excluded from the primary analysis due to age restrictions (i.e. women 34 years of age at baseline or older will not be included in the primary analysis set 'PAS year 8' for the final analysis after 8 years)², the total number of women to be enrolled into the study treatment phase is 360.

² It is assumed about 90% of women enrolled will be 18 to 32 years of age at screening, i.e. 10% of women will be 33 to 35 years old and accordingly less will be 34 to 35 years old.

Sample size characteristics regarding the analysis of the Pearl index:

This sample size will lead to an expected exposure (years 6 to 8 combined) of 832 women years (WY). Assuming a true Pearl index of 0.2,

- the upper limit of the 95% confidence interval for the PI (years 6-8) will not exceed 1 with a probability of 76%,
- the difference between the point estimate and the upper limit of the 95% confidence interval will not exceed 1 with a probability >99.9%.

Assuming a slightly higher true Pearl index of 0.3,

- the upper limit of the 95% confidence interval for the PI (years 6-8) will not exceed 1 with a probability of 55%,
- the difference between the point estimate and the upper limit of the 95% confidence interval will not exceed 1 with a probability >99.9%.

CCI

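### Does Section 10.4 need a precision statement for the Year 6 Pearl index, whose upper limit exceeds 1 even with no pregnancy?

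*Protocol*

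**What the plan says.** Protocol 10.4 opens by saying that statistical considerations did not determine the sample size. The target is 200 women completing Year 8. After allowances for dropout and for the age limit of the Year 8 primary set, "the total number of women to be enrolled into the study treatment phase is 360". The Synopsis is looser: "Approximately 360 subject to enter the treatment period".

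10.4 then describes what that size gives for the Pearl index: "This sample size will lead to an expected exposure (years 6 to 8 combined) of 832 women years (WY"). At a true index of 0.2, "the upper limit of the 95% confidence interval for the PI (years 6-8) will not exceed 1 with a probability of 76" (per cent), and "the difference between the point estimate and the upper limit of the 95% confidence interval will not exceed 1 with a probability >99.9" (per cent). At a true index of 0.3 the first probability is 55% and the second is again above 99.9%. The readable text gives figures for no other period, and the section ends in a redacted block.

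Amendment 1 added an analysis after Year 6 to support a submission for use up to 6 years (Protocol 15.1 and 15.1.1.1). Under 10.3.1.1.1, "for the analysis after 6 years of Mirena use, the primary efficacy variable is the occurrence of pregnancy within year 6 of Mirena use", and under 10.3.2.1, "The primary analysis set will be the PAS Year 6 (for the analysis after 6 years"). SAP 6.2.1 records that this result went into its own study report and will be recalculated on the final database.

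**The concern.** The Year 6 Pearl index is a primary result written for a regulatory submission, yet the only readable precision statement describes an exposure more than twice the Year 6 maximum. A reader who carried the 76% and 55% over to Year 6 would be badly misled, because at one year of follow-up the probability of meeting either yardstick is zero. It also looks as though Amendment 1 created a new primary analysis without revisiting the sample size section: 15.1.1.1 does not list 10.4 among the sections affected. What would be at stake is whether the Year 6 analysis was planned with any knowledge of how wide its interval must be.

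**Working it through.** **Inputs.** Enrolment is 360 (Protocol 10.4). The interval is two-sided 95% exact Poisson, with upper limit 0.5 × χ²(0.975, 2(x+1)) / E, where x is the number of pregnancies and E the exposure in hundreds of woman-years (Protocol 10.3.2.1, SAP 6.2.1). Also from 10.3.2.1, "one woman year is 365 days of treatment exposure". A woman who continues into Year 7 contributes 365 days to the 1-year index (Protocol Table 10–1, SAP Table 6–1). The numerator 0.5 × χ² is 3.689, 5.572, 7.225 and 8.767 for x = 0, 1, 2 and 3.

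**The plan's own figures.**
- Exposure: 10.4 gives no time unit for its 15% dropout. Read as per year, with 350 women and mid-year averaging, the three years give 323.75 + 275.19 + 233.91 = 832.8 woman-years, against 832 stated.
- Upper limit at 832 woman-years: 7.225/8.32 = 0.868 for x = 2 and 8.767/8.32 = 1.054 for x = 3. Staying at or below 1 therefore needs at most 2 pregnancies.
- True index 0.2: mean 0.2 × 8.32 = 1.664, and P(X ≤ 2) = 76.7% (stated 76%).
- True index 0.3: mean 2.496, and P(X ≤ 2) = 54.5% (stated 55%).
- Upper limit minus estimate at most 1: this holds for x ≤ 9, with probability 99.999% and 99.97% (stated above 99.9%).

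Everything stated is right for the period named, to within one percentage point.

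**Year 6.**
- Ceiling: 360 × 365/365 = 360 woman-years. Dropout, the age limit and excluded back-up periods can only lower it.
- x = 0: 3.689/3.60 = 1.02. x = 1: 5.572/3.60 = 1.55.
- A zero-event upper limit of 1 needs 368.9 woman-years.
- Upper limit minus estimate: 1.02 for x = 0 and 1.55 − 0.28 = 1.27 for x = 1. Zero events is the easiest case here too.
- Both yardsticks therefore have probability 0 at Year 6, whatever the true index.
- With 15% dropout per year (an assumption), exposure is (360 + 306)/2 = 333 woman-years and the zero-event limit is 3.689/3.33 = 1.11.

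**Would a larger trial help?** At the same assumed dropout, 368.9/0.925 = 398.8, so 399 women would be needed. Even then the limit stays at or below 1 only with no pregnancy. That has probability exp(−0.738) = 48% at a true index of 0.2, and 33% at 0.3.

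**What the plan does with the result.** The SAP analyses all variables descriptively (4.1). No readable section of either document sets a limit that the Pearl index must meet at Year 6, Year 7 or Year 8. Where a criterion was wanted, one was written: Amendment 1 added an upper confidence limit of 35% for the heavy menstrual bleeding endpoint (Protocol 15.1.1.11). For Year 6 the plan reports the index with its exact interval.

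**The case for a change.** The best case for a change is that a primary estimate meant for a regulator should come with its expected precision. None is readable in Protocol 10.4, Protocol 10.5 or SAP 4.6, and one sentence would supply it at no cost. The redaction at the end of 10.4 is unlikely to hold Year 6 figures, because 10.4 is missing from the section-by-section list of Amendment 1 changes in Protocol 15.1.2. The target of approximately 360 does not rescue Year 6 either: 369 women would have to complete the year with no back-up use.

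The arithmetic in that case stands, and so does the observation that the readable text is silent on Year 6. It does not show that anything is wrong. The 10.4 figures carry their period in their own wording, so nobody is told that they apply to a single year. The zero probability is also partly a threshold effect: at the ceiling the limit misses 1 by 0.02, on a yardstick written for a three-year index. The practical content is that one year gives a wider interval than three, and the reported interval shows that.

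Further requests would not improve the plan. The Year 6 database was locked before SAP v3.0 of 21 August 2019, and the result has been reported, so a standard for an adequate Year 6 result would now be set with the result known. The Year 7 analysis was planned before Amendment 1 (old text in Protocol 15.1.2.34), so its precision may already sit in the redacted block. A figure such as 333 woman-years should not be written into 10.4 while the time unit of the 15% is unstated.

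**Conclusion.** No change is needed. This is missing detail whose addition would gain nothing. The Year 6 analysis is imprecise: at most 360 woman-years, and an upper limit of at least 1.02 with no pregnancy. But 1 is a planning yardstick for Years 6 to 8 and not a success criterion, and the stated precision is correct for that period. Followed exactly as written, the plan gives the same Year 6 estimate and interval with or without a note, and any reader of that interval sees how wide it is. A sentence in 10.4 confining its probabilities to the final analysis would be harmless but optional.

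The conclusion rests on 360 women, the planned two-sided 95% exact interval and the readable text of 10.4. The 1.02 is a lower bound that needs no assumption about dropout or back-up use. The 1.11 assumes 15% dropout per year.

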10.5 Planned interim analyses

This section was changed in Amendment 1, see Section 15.1.1.1.

No formal interim analysis in the sense of a group sequential or adaptive design is planned. However, an analysis of the data is planned after Year 6, including all subjects who have prematurely discontinued or completed Visit 4, i.e. treated with Mirena for up to 6 years (1 year in the study). Another analysis of the data is planned after Year 7, including all subjects who have prematurely discontinued or completed Visit 6, i.e. treated with Mirena for up to 7 years (2 years in the study).

11. Data handling and quality assurance

11.1 Data recording

This section was changed in Amendment 1, see Section 15.1.1.23.

The data collection tool for this study will be eCRF; a validated electronic data capture system called RAVE. Subject data necessary for analysis and reporting will be entered/transmitted into a validated database or data system (e.g. CIE/TOSCA; SAS).

Data will be entered by site personnel into an internet based electronic data capture software system RAVE, which Covance has licensed from Medidata Solutions Worldwide. RAVE has been validated by Medidata Solutions Worldwide and Covance for use in its clinical studies. RAVE allows for the application of software logic to set-up data entry screens and data checks to ensure the completeness and accuracy of the data entered. Covance extensively applies the logic to ensure data are complete and reflect the requirements of the study. Queries resulting from the application of the software logic are resolved by site personnel. The data are stored at a secure host facility maintained by Medidata Solutions Worldwide and transferred on a periodic basis to Covance's internal computer system via a secure Virtual Private Network.

Access to RAVE is through a password-protected security system. All personnel are thoroughly trained before acquiring access to the system. Training records are maintained.

Personnel with access to RAVE are supported by a Service Desk to answer questions and ensure access is maintained such that data entry can proceed in a timely manner.

RAVE contains a system-generated audit trail that captures any changes made to a data field, including who made the change, why it was changed, and the date and time it was made. This information is available both at the investigator's site and at Covance.

Data entries are supported by source documents maintained for all subjects. A source document checklist will be used at the site to identify the source data for key data points collected and the monitor will work with the site to complete this.

Source documentation

The site must implement processes to ensure availability of all required source documentation. A source document checklist (not part of this protocol) will be used at the site to identify the source data for key data points collected and the monitor will work with the site to complete this.

It is the expectation of the sponsor that all data entered into the CRF has source documentation available at the site except for the data listed below which will be entered directly into the CRF; thus, these CRF data will be the source and no additional source documentation will be available. The data entered directly into the CRF is not needed for the subject's routine medical care.

- data fields to be completed directly in the eCRF:

- assessments on Mirena removal by subject (pain) and investigator (ease of removal), and
- subject's satisfaction with Mirena.

These will be entered into eCRF by the investigator.

eDiary data

The eDiary entries will be considered as primary source data.

Data recorded from screening failures

At minimum, the following data should be recorded in the CRF:

- Demographic information (subject number; year of birth / age; if applicable race / ethnicity)
- Date for Mirena insertion
- Indication for Mirena
- Reproductive and menstrual history
- Date of informed consent
- Relevant inclusion/exclusion criteria
- Reason for premature discontinuation
- Date of last visit.

These data will be transferred to the respective database.

For screening failures with an SAE or pregnancy (see also section 9.4.1), the following data should be collected in the CRF in addition to the data specified above:

- All information related to the SAE/pregnancies such as:
 - The SAE itself / pregnancy test evaluation page
 - Concomitant medication
 - Medical history
 - Other information needed for SAE complementary page

11.2 Monitoring

In accordance with applicable regulations, GCP, and sponsor's/CRO's procedures, monitors will contact the site prior to the start of the study to review with the site staff the protocol, study requirements, and their responsibilities to satisfy regulatory, ethical, and sponsor's requirements. When reviewing data collection procedures, the discussion will also include identification and documentation of source data items.

The sponsor/designee will monitor the site activity to verify that the:

- Data are authentic, accurate and complete.
Supporting data may be requested (example: blood glucose readings to support a diagnosis of diabetes).
- Safety and rights of subjects are being protected
- Study is conducted in accordance with the currently approved protocol (including study treatment being used in accordance with the protocol)
- Any other study agreements, GCP, and all applicable regulatory requirements are met.

The investigator and the head of the medical institution (where applicable) agrees to allow the monitor direct access to all relevant documents.

11.3 Data processing

Data will be collected as described in Section 11.1. Clinical data management will be performed in accordance with applicable sponsor's/CRO's standards and data cleaning procedures. This is applicable for data recorded on eCRF as well as for data from other sources (e.g. laboratory, ePRO).

For data coding (e.g. AEs, medication), internationally recognized and accepted dictionaries will be used.

After its initial release for biometrical analysis, the clinical database is planned to be re-opened for the inclusion of the following additional data: e.g. pharmacokinetic data, residual content data and post study pregnancy tracking data.

11.4 Missing data

Most important is to avoid missing data, e.g. by monitoring in time for completeness (see Section 11.2) and investigators' training, especially by instructing them to motivate subjects to be compliant with the study protocol. If the subject is unable to come to on-site visit during the allotted timeframe, the visit may be documented via phone as described at Section 6.4.1 in order to collect as much data as possible. In addition, for completing the eDiary, 72-hour recall time is implemented to allow some flexibility for eDiary completion and to avoid missing eDiary data.

11.5 Audit and inspection

To ensure compliance with GCP and regulatory requirements, a member of the sponsor's (or a designated CRO's) quality assurance unit may arrange to conduct an audit to assess the performance of the study at the study site and of the study documents originating there. The investigator/institution will be informed of the audit outcome.

In addition, inspections by regulatory health authority representatives and IEC(s)/IRB(s) are possible. The investigator should notify the sponsor immediately of any such inspection.

The investigator/institution agrees to allow the auditor or inspector direct access to all relevant documents and allocate his/her time and the time of his/her staff to the auditor/inspector to

discuss findings and any issues. Audits and inspections may occur at any time during or after completion of the study.

11.6 Archiving

Essential documents shall be archived safely and securely in such a way that ensures that they are readily available upon authorities' request.

Patient (hospital) files will be archived according to local regulations and in accordance with the maximum period of time permitted by the hospital, institution or private practice. Where the archiving procedures do not meet the minimum timelines required by the sponsor, alternative arrangements must be made to ensure the availability of the source documents for the required period.

The investigator/institution notifies the sponsor if the archival arrangements change (e.g. relocation or transfer of ownership).

The investigator site file is not to be destroyed without the sponsor's approval.

The contract with the investigator/institution will contain all regulations relevant for the study center.

12. Premature termination of the study

The sponsor has the right to close this study (or, if applicable, individual segments thereof [e.g. treatment arms; dose steps; centers]) at any time, which may be due but not limited to the following reasons:

- If risk-benefit ratio becomes unacceptable owing to, for example,
 - Safety findings from this study (e.g. SAEs)
 - Results of any interim analysis
 - Results of parallel clinical studies
 - Results of parallel animal studies
(on e.g. toxicity, teratogenicity, carcinogenicity or reproduction toxicity).
- If the study conduct (e.g. recruitment rate; drop-out rate; data quality; protocol compliance) does not suggest a proper completion of the trial within a reasonable time frame.

The investigator has the right to close his/her center at any time.

For any of the above closures, the following applies:

- Closures should occur only after consultation between involved parties. Final decision on the closure must be in writing.
- All affected institutions (e.g. IEC(s)/IRB(s); competent authority(ies); study center; head of study center) must be informed as applicable according to local law.
- All study materials (except documentation that has to remain stored at site) must be returned to the sponsor. The investigator will retain all other documents until notification is given by the sponsor for destruction.
- In the event of a partial study closure, ongoing subjects, including those in post study follow-up, must be taken care of in an ethical manner.

Details for individual subject's withdrawal can be found in Section 6.4.1.

13. Ethical and legal aspects

